### **SECTION 3.3 Study design**

This study is a feasibility study as defined by the NIHR – a study conducted to provide further information about certain parameters to inform a future larger study, as opposed to a pilot study in which all aspects of a full study are conducted in a miniature form.

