#### **4.4b Secondary outcomes**

- Acceptability of outcome data collection by participants defined as the % completion of the PROMs outlined below.
- The Tegner Activity Scale measures activity on a scale from 0-10, with higher scores indicating higher activity. It has shown good reliability and content validity in patients with acute patellar dislocation and prior dislocation/subluxation and shown to measure a distinct aspect of recovery demonstrated by its low correlation with knee specific and general health questionnaires in this cohort. It has previously been used to assess the effect of conservative management in patients with first

time LPD patients. It will be completed after informed consent has been obtained prior to the first physiotherapy session based on **pre-injury** activity levels and at 3 months after the first physiotherapy session based on their activity levels at that time. It will be administered as a patient completed questionnaire. The change in Tegner Activity Scale scores will be used for analysis.

[figure not shown]
- The Lysholm Knee Scoring Scale was originally developed for patients with knee ligament injuries and subsequently revised. It is scored from 0-100 with lower scores indicating higher pain and disability. It has since demonstrated good test-retest reliability in patients with first time LPD and prior subluxation/dislocation and was able to discriminate between those who subsequently developed recurrent instability and those who did not. It has been used to assess the effect of conservative management in patients with first time LPD and recurrent LPD. It will be completed after informed consent has been obtained prior to the first physiotherapy session and 3 months after the first physiotherapy session based on **current** knee symptoms at that time. It will be administered as a patient completed questionnaire. The change in Lysholm Knee scores will be used for analysis.
- The EQ-5D is a commonly used quality of life questionnaire. It will be completed after informed consent has been obtained prior to the first physiotherapy session and 3 months after the first physiotherapy session based on **current** symptoms at that time. It will be administered as a patient completed questionnaire. The change in EQ-5D scores will be used for analysis.

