## **SECTION 4.6 Sample size**

### **4.6a Target sample size**

Data we collected from the John Radcliffe trauma service for 2017 conservatively estimates 31 LPD patients match our eligibility criteria and 51 LPD patients are of unknown eligibility, due to the required information not being available in the patient's medical records. Of those of unknown eligibility, 23 are due to the direction of dislocation not being reported. As medial patellar dislocations are exceedingly rare a conservative estimate would be 54 eligible participants per year and 27 for our planned recruitment period of 6 months.

We aim to recruit 15 participants over 6 months. Recruitment will cease at the end of the designated recruitment period of 6 months or earlier if the target of 15 participants is achieved.

Previous trials in the UK investigating conservative interventions for this condition have reported low recruitment rates but not explicitly stated what these rates were. This makes it difficult to estimate recruitment rates for this study and why it forms one of our primary objectives. We feel a recruitment target of 15 participants is feasible due to our conservative estimate of eligible participants and the broader inclusion criteria in our study compared to previous studies.

As this is a feasibility study, no power calculation has been performed. A sample size of 15 is a pragmatic choice. This has been used for a study similar to ours, a single group prospective study investigating the acceptability and feasibility of exercise for patients with endometrial cancer.

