## **SECTION 5.3 Statistical methods**

### **5.3a Statistical Methods for analysing primary and secondary outcomes**

Statistical methods and results will be reported, where possible, in accordance with SAMPL guidelines. All analyses will be conducted using the latest version of SPSS (IBM Corp. Armonk, NY).

Eligibility, recruitment, acceptability and adherence will be described using descriptive statistics and expressed as integers and percentages where relevant.

Tegner Activity scores will represent ordinal data. Baseline and 3 months post 1st physiotherapy session scores will be described using descriptive statistics using median and inter-quartile range.

Lysholm scores will represent continuous data. Baseline and 3 months post 1st physiotherapy session scores will be described using descriptive statistics using mean and standard deviations if scores are normally distributed or median and inter-quartile range if data is skewed.

EQ-5D-5L scores will represent continuous data. Baseline and 3 months post 1st physiotherapy session scores will be described using descriptive statistics using mean and standard deviations if scores are normally distributed or median and inter-quartile range if data is skewed.

Patient satisfaction scores will be described using descriptive statistics. Ordinal data will be expressed using medians and inter-quartile ranges, and categorical data will be expressed as integers and percentages.

Baseline characteristics and additional outcome data on intervention delivery and harms will be expressed using descriptive statistics. Continuous variables will be described using means and standard deviations for normal distributions or medians and inter-quartiles range for non-normal distributions. Categorical data will be expressed as integers and percentages.

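### Section 5.3a lets an unspecified normality judgement on at most 15 values decide between mean (SD) and median (IQR), so the SD of Lysholm or EQ-5D-5L may go unreported

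*Combined protocol and SAP*

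**What the plan says.** Section 5.3a classifies both instruments the same way: "Lysholm scores will represent continuous data" and "EQ-5D-5L scores will represent continuous data". For each, the baseline and 3-month scores are to be described by "mean and standard deviations if scores are normally distributed or median and inter-quartile range if data is skewed". A third statement covers baseline characteristics, intervention delivery and harms. There, continuous variables get means and SDs if normal, or "medians and inter-quartiles range for non-normal distributions". Tegner is outside the rule, being fixed at median and IQR.

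The section names no test, plot or threshold. It does not say whether normality is judged once per outcome or once per visit, and it does not require an SD in every case.

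Three other places bear on the point:

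- Section 4.4b: "The change in Lysholm Knee scores will be used for analysis", with a matching statement for EQ-5D. Section 5.3a gives no summary for a change score.
- Section 4.6a: "We aim to recruit 15 participants over 6 months" and "As this is a feasibility study, no power calculation has been performed. A sample size of 15 is a pragmatic choice".
- Section 3.3 adopts the definition of a feasibility study as "a study conducted to provide further information about certain parameters to inform a future larger study".

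**The concern.** The rule makes the reported statistic depend on the sample that it describes, and with 15 or fewer values the sample says little about the shape of the distribution. Two consequences follow.

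First, whenever the scores are judged skewed, the plan drops the SD. A later study that took Lysholm or EQ-5D-5L as an outcome would usually want that figure for its sample size.

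Second, if each visit is judged on its own, a baseline mean could stand beside a 3-month median. Those two numbers cannot be subtracted to give a change, although Section 4.4b names change for analysis. Section 4.4b gives Lysholm a range of 0 to 100 with low scores worse, so a fairly symmetric baseline soon after injury and a follow-up crowded towards 100 is a plausible pattern.

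**Working it through.** **Figures in the plan.** No formula lies behind the target of 15, so there is nothing to reproduce; it serves here only as the largest possible number of values per visit. The eligibility arithmetic beside it in Section 4.6a does reproduce: 31 + 23 = 54 per year, and 54/2 = 27 in six months.

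**Inputs.**

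- n = 15 per visit (Section 4.6a).
- n = 7 as a pessimistic case at 3 months. Section 3.1b reports 52% attrition in an earlier exercise trial, and 15 × 0.48 = 7.2. The plan assumes no such loss for this study.
- Assumed, because the plan gives none: the criterion (Shapiro-Wilk p < 0.05, or alternatively absolute sample skewness above 1), the score distributions, and a correlation of 0.5 between visits.

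**Step 1: how often one set of scores is judged non-normal** (simulation)

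| True distribution | n | Shapiro-Wilk | abs. skewness > 1 |
|---|---|---|---|
| Normal | 15 | 5% | 9% |
| Beta(5,2), mild skew | 15 | 12% | 16% |
| Beta(5,1.8), moderate skew | 15 | 15% | not run |
| Gamma, skewness 1 | 15 | 21% | not run |
| Beta(5,1.2), ceiling | 15 | 34–36% over repeat runs | not run |
| Beta(4,1), ceiling | 15 | 42% | 40% |
| Normal | 7 | 5% | 21% |
| Beta(4,1), ceiling | 7 | 16% | 36% |

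A distribution with a clear ceiling is called normal more often than not, and at n = 7 the skewness criterion calls truly normal data skewed in about one sample in five.

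**Step 2: chance that the two visits get different summaries, if judged separately.** With flagging probabilities p0 and p1, and ignoring the correlation, this is p0(1 − p1) + p1(1 − p0).

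- Both normal: 2 × 0.05 × 0.95 = 0.095. Simulated with correlation 0.5: 9 to 11% (skewness criterion 15%).
- Normal baseline, Beta(5,1.2) follow-up: 0.05 × 0.64 + 0.36 × 0.95 = 0.374. Simulated: 36 to 38%.
- Normal baseline, Beta(4,1) follow-up: 0.05 × 0.58 + 0.42 × 0.95 = 0.428. Simulated: 43% (skewness criterion 42%).
- Beta(5,1.8) at both visits: about 25%, simulated.

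**Step 3: chance that at least one visit is flagged, so that an SD is dropped.** This is 1 − (1 − p0)(1 − p1), again ignoring the correlation.

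- Both normal: 1 − 0.95² = 0.098. Simulated: 9% (skewness criterion 16%).
- Normal baseline, Beta(4,1) follow-up: 1 − 0.95 × 0.58 = 0.449. Simulated: about 45% under either criterion.

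Step 3 does not need separate decisions. If a flag at either visit sent the whole outcome to medians, the same probabilities would apply and both SDs would be dropped.

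**Step 4: what the SD would be worth.** The 95% interval for an SD, as a multiple of the estimate, runs from √[(n − 1)/χ²(0.975)] to √[(n − 1)/χ²(0.025)]. At n = 15 this is √(14/26.12) = 0.73 to √(14/5.63) = 1.58. At n = 7 it is 0.64 to 2.20.

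**The case against.** The best reply is that this is a reporting preference about secondary, descriptive outcomes. The stated objective for the questionnaires in Section 3.2b is completion rates. No listed objective is to estimate an SD, and Section 5.3b treats the choice of outcome instruments for a future study as still open. No hypothesis test or feasibility decision turns on the summary chosen. All of that stands, and it limits the severity.

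Four stronger readings are tempting, and the documents do not support them.

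- *That normality is judged separately at each visit.* In Section 5.3a one sentence per instrument takes both visits as its subject under one condition, so a single decision per outcome is at least as natural. On that reading the mismatch in Step 2 disappears; the risk in Step 3 does not.
- *That the judgement is a coin toss.* Under moderate skew the assumed test flags 15 to 21% of samples, so it mostly misses the skew and the mean and SD are mostly reported. A weak test lowers the chance of losing the SD without removing it. Higher mismatch rates can be produced with heavily right-skewed distributions, but those lean away from the Lysholm ceiling and are not relevant.
- *That the study fails its purpose without an SD.* The need is an inference from the general aim in Section 3.3.
- *That the SD would be lost for good.* Anonymised data are kept for 10 years (Section 5.2b) and may be shared with consent (Section 7.6). Recovery is possible, but a reader of the published report would not have the figure.

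The SD would also be imprecise. At n = 15 the variance interval spans a factor of 26.12/5.63 = 4.6. That is a reason to report it with its n, and no reason to omit it.

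**Conclusion.** The point holds as a minor one and a free improvement. The either/or rule rests on a judgement that at most 15 values cannot support, and it allows the SD of Lysholm or EQ-5D-5L to go unreported: in roughly 9 to 16% of studies when both visits are normal, and about 45% with a marked ceiling at 3 months. Different summaries at the two visits are a further possibility only if each visit is judged separately, which the text leaves open.

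Every percentage depends on the assumed criterion, distributions and correlation, and should be read as showing that the risk is not remote rather than as a forecast. The ceiling argument is documented for Lysholm only, since the protocol gives no bounds for EQ-5D-5L. Eligibility, recruitment, acceptability and adherence are not affected.

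**What to change.** Replace the conditional rule in each of the three places in Section 5.3a (Lysholm, EQ-5D-5L, other continuous variables) with a fixed set of summaries: n, mean, SD, median, IQR and range, whatever the shape of the data. For Lysholm and EQ-5D-5L, give this set at baseline, at 3 months, and for the paired change among participants with both scores. That last item supplies the summary of change that Section 4.4b calls for and Section 5.3a lacks.

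This removes the normality judgement, so the chance of an omitted SD or of mismatched visits becomes zero by construction. It does not make the SD more precise, so n should stand beside it. The cost is three edited statements and a few extra table rows, with no new data and no change to the design.

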### **SECTION 4.4 Outcomes**

#### **4.4a Primary outcomes**

- Eligibility defined as the % of participants with a diagnosis of LPD, screened for eligibility, who satisfy the eligibility criteria
- Recruitment rates defined as the % of eligible participants who consent to participate in the study
- Acceptability defined as the % attrition rate (participants who fail to complete follow up data collection at 3 months) and participant response to a patient satisfaction questionnaire
- Adherence defined as the % of scheduled physiotherapy sessions attended and participant self-reported intervention adherence defined as the % of prescribed exercise sessions completed

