## **SECTION 5 METHODS: DATA COLLECTION, MANAGEMENT, AND ANALYSIS**

### **SECTION 5.1 Data collection methods**

#### **5.1a Outcomes and time points at which they will be assessed**

Outcome	Measurement	Time point
Demographics	Age, sex, height, weight, affected knee, mechanism of injury (traumatic/atraumatic), previous history of ipsilateral patella dislocation, previous history of contralateral patella dislocation,	Baseline

	time from injury to presentation to acute care (ED or trauma services), family history of patella dislocation, employment status, level of education, ethnicity	
Assessment findings	
Presence/absence of the following on:
 
 
• A convincing patient history of a visible deformity on the lateral aspect of the knee or a sensation of the patella ‘popping’ out of joint followed by spontaneous reduction
 
• Presence of a haemarthrosis or joint effusion on clinical examination
 
• Tenderness along the medial patellofemoral complex (tenderness at the following bony landmarks or at any point extending between these two points: at or just proximal to the medial epicondyle of the femur and the midpoint of the medial aspect of the patella extending to the junction of the medial quadriceps tendon and the patella)
 
• Apprehension on laterally directed force of the patella
 
	Baseline
Eligibility	% of participants with a diagnosis of LPD who meet the eligibility criteria	Completion of study
Recruitment	
% of eligible participants who consent to participate in the study
 
Reasons for not consenting will also attempt to be collected
	Completion of study
Adherence	% of scheduled physiotherapy sessions attended	
Completion of intervention
 
3 months post first

	Participant self-reported % of prescribed home exercise sessions completed	physiotherapy session
Acceptability	% attrition rate  Patient satisfaction questionnaire	Completion of study  3 months post first physiotherapy session
Follow up	% of participants who consent to treatment who return 3 month questionnaires	Completion of study
Knee function, pain and instability	Lysholm Knee Scoring Scale	Baseline, 3 months post first physiotherapy session
Activity level	Tegner Activity Scale	Baseline, 3 months post first physiotherapy session

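### For ordinal satisfaction items, section 5.3a commits only to median and inter-quartile range, which with 15 responders can leave up to three of the lowest answers unseen

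*Combined protocol and SAP*

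**What the plan says.** Section 4.4a defines acceptability by two measures, the attrition rate and "participant response to a patient satisfaction questionnaire". Section 5.1a lists the questionnaire in the acceptability row, to be collected 3 months after the first physiotherapy session. Section 3.2a says it is designed internally. Its items, response options and scoring do not appear in the document.

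Section 5.3a contains two sentences that bear on how it is summarised. The general one covers four primary outcomes together: "Eligibility, recruitment, acceptability and adherence will be described using descriptive statistics and expressed as integers and percentages where relevant". The later one, in the paragraph on patient satisfaction scores, is specific: "Ordinal data will be expressed using medians and inter-quartile ranges, and categorical data will be expressed as integers and percentages".

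On size, section 4.6a states: "Recruitment will cease at the end of the designated recruitment period of 6 months or earlier if the target of 15 participants is achieved". It gives no statistical basis for that number: "As this is a feasibility study, no power calculation has been performed. A sample size of 15 is a pragmatic choice". Section 3.2 states that no numerical feasibility targets have been set.

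**The concern.** Whether a programme is acceptable depends largely on how many people found it unacceptable, that is, on the lower tail of the answers. A median with quartiles describes the middle half and, in a small sample, is unaffected by the few lowest values. The specific sentence in 5.3a assigns counts to categorical items and median with inter-quartile range to ordinal ones. On its ordinary reading it promises no category table, minimum or range for ordinal items.

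Satisfaction is the part of acceptability that asks participants directly, and attrition cannot replace it. Under section 5.1d, someone who stops treatment but still gives follow-up data is not counted as a withdrawal. A dissatisfied participant who returns the form is therefore retained for the attrition figure. Adherence may show that this person stopped, but the stated dissatisfaction would be seen only in the satisfaction items. With no thresholds set, the judgement on acceptability rests on what the descriptive tables show.

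**Working it through.** **Inputs.**
- Maximum number of responders: 15 (section 4.6a).
- Summary: median and inter-quartile range (section 5.3a).
- Software: "All analyses will be conducted using the latest version of SPSS (IBM Corp. Armonk, NY"). The percentile definition is not stated. I assume position (n+1)p and check alternatives below.
- Response scale: not given. The 5-point scale (1 = worst) used in the examples is an assumption. The order-statistic limit itself does not depend on the scale.

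**The plan's own figures.** The target of 15 is not derived, so there is nothing to reproduce for it. The one calculation in 4.6a reproduces: 31 + 23 = 54 eligible per year, and 54/2 = 27 in 6 months. Reaching 15 needs 15/27 = 56% of them to consent, so fewer than 15 responders is a realistic possibility.

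**Limit at n = 15.** The quartile positions are 16 × 0.25 = 4, 16 × 0.5 = 8 and 16 × 0.75 = 12. The three lowest ordered values enter none of these, so they can be any lower value: 3/15 = 20%.

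**Limit at smaller n.** The lowest ordered value used has rank floor((n+1)/4), so the number that can go unseen is floor((n+1)/4) − 1.

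| Responders | (n+1)/4 | Lowest answers unseen | Share |
|---|---|---|---|
| 15 | 4 | 3 | 20% |
| 11 to 14 | 3 to 3.75 | 2 | 18% to 14% |
| 7 to 10 | 2 to 2.75 | 1 | 14% to 10% |
| 6 | 1.75 | 0 | 0% |

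**Other quartile definitions.** At n = 15, Tukey hinges and 8 of 9 standard quantile definitions (the assumed one among the 8) give 3, and the ninth gives 2. At smaller n some definitions differ from the table by one. For example, Tukey hinges give 3 at n = 13 and 14, and 2 at n = 9 and 10.

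**Illustration (assumed 5-point item).** Nine 4s and six 5s give median 4, quartiles 4 and 5. Changing one, two or three of the 4s to 1 gives the same summary. A fourth moves the lower quartile to 1 under (n+1)p, or to 2.5 under Tukey hinges.

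**How far this depends on the distribution.** Let any three of the 15 people change their answer to 1. There are C(15,3) = 455 choices.
- In the clustered example above, the summary changes only if all three came from the six 5s: C(6,3) = 20 choices. It is unchanged in 455 − 20 = 435.
- In a more mixed example (one 2, three 3s, six 4s, five 5s; median 4, quartiles 3 and 5), the person answering 2 must be one of the three, and the other two must not both come from the five 5s: C(14,2) − C(5,2) = 91 − 10 = 81. It is unchanged in only 81 of 455.

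**What counts would show.** Three of 15 would appear as 3/15 = 20.0% (exact 95% interval 4.3% to 48.1%), against 0/15 = 0% (upper 97.5% limit 21.8%). The counts are imprecise at this size, but the three answers would be visible.

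**The case against.** Median and inter-quartile range is a conventional summary for ordinal data, and asking for a frequency table in a descriptive single-group study of 15 can be called a presentation preference. That is fair as to seriousness: this is not an analysis error. Three stronger readings are also tempting, and the document does not support them.

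- A reader might infer that the plan excludes category counts. It does not. The general sentence in 5.3a allows them for acceptability, which includes satisfaction, and categorical satisfaction items receive them anyway. What stands is that nothing commits to counts for ordinal items, and the specific sentence points the other way.
- A reader might infer that people lost to follow-up vanish from the report. They do not. Attrition is reported as a percentage, 5.1a has a separate row for return of the 3-month questionnaires, and 5.3b reports missingness by questionnaire and item. If 11 of 15 responded to follow-up, attrition would read 4/15 = 27%. Section 5.1d also seeks follow-up data from people who leave treatment, so they may be in the summary. What stands is small: no section places the number responding beside the satisfaction result.
- A reader might infer that the study would declare the intervention acceptable, or that its primary result would not change. No threshold exists (section 3.2), and satisfaction is one component of one of four primary outcomes, read alongside attrition and adherence.

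The limit of three is also a maximum on an instrument that cannot be seen. If every item turns out to be yes/no or otherwise categorical, the plan already gives counts.

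**Conclusion.** The point holds in a limited form. For ordinal satisfaction items the plan commits only to a summary that, with 15 responders, can leave up to 3 of the lowest answers (20%) without effect; with 11 to 14 responders the figure is 2, and with 7 to 10 it is 1. These limits assume the (n+1)p quartile definition and that the questionnaire contains ordinal items. They are ceilings: masking is likely when most answers cluster near the top and much less likely when they are mixed. The consequence is that the satisfaction summary could hide a minority who found the programme unacceptable, including people whom attrition counts as retained. It does not follow that the study would reach a wrong conclusion, because the other reported measures remain and no decision rule depends on the median.

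**What to change.** In section 5.3a, state that each ordinal satisfaction item will be reported as n (%) in every response category, with the number of responders out of those enrolled shown beside it. The median and inter-quartile range may be kept as an addition. This also settles which of the two sentences in 5.3a governs satisfaction data. It needs no new data, participants or analysis; the only cost is a larger table.
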